### 10.1.2 REDUCTION

- Intrapatient dose reduction by 1, and if needed 2- dose level(s) will be allowed (see Table below) depending on the type and severity of toxicity encountered provided that criteria for patient withdrawal from study treatment have not been met.
- All intra-patient dose reductions are relative to the lowest dose level of the current cycle.
- No more than 2 dose reductions are permitted in any patient. If further dose reduction is required, the patient must be removed from further BCG administration.
- The dosing period may be extended for BCG as outlined in section above
- The below table describes the recommended dose modifications for study treatment associated toxicity.

TABLE: DOSE MODIFICATION FOR BCG BASED ON TOXICITY AND GRADE

## [name], Phase II Study of BCG followed by Sunitinib for High risk NMIBC

\* treatment is based on type of infection

# if BCG infection of grade 3 or 4 occurs during the 1st induction course, patients will be withdrawn from the study and replaced. Otherwise, patients will be offered alternative therapy at the discretion of the treating clinician and followed for appropriate endpoints.

### 10.2 SUNITINIB: In the event of any (CTC version 3) drug related grade 3 or 4 non-hematologic or

Toxicity	Grade 1	Grade 2	Grade 3	Grade 4
Irritative Bladder symptoms	Continue at the same dose level	Continue at the same dose level.	Dose reduction to -1. If Grade 3 toxicity persists, reduction to -2. Discontinuation will occur at the discretion of the treating clinician.	Dose reduction to -1. If Grade 4 toxicity persists, reduction to -2. Discontinuation will occur at the discretion of the treating clinician.
Fever, chills and "flu-like" symptoms	Continue at same dose level.	Continue at same dose level.	Dose reduction to -1. If Grade 3 toxicity persists, reduction to -2. Discontinuation will occur at the discretion of the treating clinician	Dose reduction to -1. If Grade 4 toxicity persists, reduction to -2. Discontinuation will occur at the discretion of the treating clinician
Occular symptoms +/- joint symptoms	Continue at the same dose level.	Continue at the same dose level.	Dose reduction to -1. If Grade 3 toxicity persists, reduction to -2. Discontinuation will occur at the discretion of the treating clinician	Dose reduction to -1. If Grade 4 toxicity persists, reduction to -2. Discontinuation will occur at the discretion of the treating clinician
Infection	Treat* and continue at same dose after resolution of symptoms within 2 weeks	Treat* and continue at same dose after resolution of infection within 2 weeks	Withdraw BCG treatment#	Withdraw BCG treatment#

grade 4 hematologic adverse event(s) drug should be held until the toxicity resolves to < grade 1 and then the drug should be restarted at -1 dose level (see 6.1).

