## 8.0 CRITERIA FOR REMOVAL FROM STUDY:

8.1 Protocol therapy will be discontinued and patients will be removed from study based on any of the following criteria (Patients clinical course will be followed for two years.):

- Patients' wishes.
- Disease progression as documented by 3 month or 6 month bladder tumor biopsy documenting progression to muscle invasive bladder cancer.
- Clinician and patient determine that alternative treatment plan should be pursued. Reason for pursuing alternative therapy will be documented.
- Intercurrent illness that prevents further administration of treatment.
- Unacceptable adverse event(s) that may or may not be directly related to BCG and/or sunitinib but that in the judgment of the treating physician make it dangerous for the patient to be retreated.
- General or specific changes in the patient's condition that render the patient unacceptable for further treatment in the judgment of the investigator.

8.2 As an excessive rate of withdrawals can render the study un-interpretable, unnecessary withdrawal of patients should be avoided.

8.3 When a patient discontinues treatment early, the Investigator will make every effort to contact the patient and to perform a final evaluation. The reason(s) for withdrawal will also be recorded. The reason for terminating therapy should be clearly recorded.

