#### 10.2.1 DOSE REDUCTION FOR SUNITINIB

- Intrapatient dose reduction by 1, and if needed 2- dose level(s) will be allowed (see 6.1) depending on the type and severity of toxicity encountered provided that criteria for patient withdrawal from study treatment have not been met.
- All intra-patient dose reductions are relative to the lowest dose level of the current cycle.
- Recovery to acceptable levels of toxicity must occur within 4 weeks to allow continuation in the study.

[name], Phase II Study of BCG followed by Sunitinib for High risk NMIBC

- No more than 2 dose reductions are permitted in any patient. If further dose reductions are required, patients will discontinue sunitinib therapy. They will continue to be followed per protocol.
- The following table describes the recommended dose modifications for study treatment associated toxicity.

TABLE: DOSE MODIFICATION OF SUNITINIB BASED ON TOXICITY AND GRADE

Recurring grade 3 toxicity requires dose reduction \* Patients who develop grade 3 or 4 hyperlipasemia or hyperamylasemia without clinical or other evidence of pancreatitis, or grade 4 hyperuricemia or grade 3 hypophosphatemia without clinical symptoms may continue study treatment without interruption. \*\*\* Patients with recurrent grade 3 lymphopenia and anemia do not require dose modification. Recurring grade 4 neutropenia or grade  $\geq 3$ thrombocytopenia persisting for at least 5 days requires dose reduction in the next cycle. Grade 4 lymphopenia does not require dose reduction.

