**Management of cardiac ejection fraction.**

Toxicity	Grade 1	Grade 2	Grade 3	Grade 4
Non-hematologic	Continue at the same dose level	Continue at the same dose level.	Withhold dose until toxicity is grade $\leq 1$ , or has returned to baseline, then resume treatment at the same dose level or reduce the dose by 1 level at the discretion of the investigator*.	Withhold dose until toxicity is grade $\leq 1$ , or has returned to baseline, then reduce the dose by 1 level and resume treatment, or discontinue at the discretion of the investigator*.
cardiac toxicity:	Continue at the same dose level.	Continue at the same dose level except in the event of Non-urgent ventricular paroxysmal dysrhythmia requiring intervention, Withhold dose until toxicity is grade $\leq 1$ , then reduce dose by 1 level and resume treatment.	Remove from further therapy, follow for applicable endpoints	Remove from further therapy, follow for applicable endpoints
Neurotoxicity	Continue at the same dose level.	Withhold dose until toxicity is grade $\leq 1$ , then continue at same dose level.	Withhold dose until toxicity is grade $\leq 1$ , then reduce the dose by 1 level and resume treatment.	Remove from further therapy, follow for applicable endpoints
Fever, chills and "flu-like" symptoms	Continue at same dose level.	Continue at same dose level.	Withhold dose until toxicity is grade $\leq 2$ , or has returned to baseline, then resume treatment at the same dose level.	Withhold dose until toxicity is grade $\leq 2$ , then reduce the dose by 1 level and resume treatment.
Hematologic	Continue at the same dose level.	Continue at the same dose level.	Withhold dose until toxicity is grade $\leq 2$ , or has returned to baseline, then resume treatment at the same dose***.	Withhold dose until toxicity is grade $\leq 2$ , then reduce the dose by 1 level and resume treatment***.

All patients will undergo a MUGA scan prior to enrollment in the study. Patients proceeding to a second cycle of therapy (BCG followed by sunitinib) will undergo a MUGA scan prior to initiation of the second cycle. Patients with an ejection fraction lower than the institutional lower limit of normal will not receive further study treatment per protocol and will be offered alternative therapy as directed by the treating clinician.

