## 13.0 STUDY CALENDAR:

[name], Phase II Study of BCG followed by Sunitinib for High risk NMIBC

		Week 1-6 BCG Course 1		Week 8-12† Sunitinib cycle 1			TURBT or bladder biopsy	Therapeutic Plan			
Required studies	Pre-study	Week1	Week 6	Week 8	Week 10	Week 12	Week 14	1. Residual/Recurrent disease without progression: a. Negative MUGA scan-if positive, proceed to 3. b. 2 nd cycle of BCG followed by sunitinib (as per week 1-14) c. alternative treatment plan per treating clinician 2. No residual disease (Calendar 2): patient will proceed to maintenance BCG therapy per institutional standard a. alternative therapy may be chosen on maintenance at patient/physician discretion 3. Disease progression or patient/clinician desire: proceed to alternative treatment per standard of care			
PHYSICAL											
History and Physical	x			x	x	x					
ECOG performance status	x			x	x	x					
Medication check	x			x	x	x					
Toxicity assessment											
LABORATORY/ STUDIES											
CBCPD	x			x	x	x					
Comprehensive panel	x			x		x					
Magnesium				x		x					
EKG	x										
Dipstick Urine		x	x								
Urine cytology*	x						x				
PT/PTT	x					x					
TSH	x										
MUGA Scan	x										
SPECIMEN SAMPLES											
Urine*		x 	x 	x		x	x				
Bladder biopsy							x				
Serum		x 	x 	x		x					
X-RAYS AND SCANS											
Chest radiograph	x										
CT or MRI abdomen/ pelvis or IVP	x										
Cystoscopy or report confirming eligibility	x										
Drug: Sunitinib				x							
Dispense BP log, Study drug info, and medication diary				x							

\* voided urine cytology obtained in clinic, instrument urine cytology obtained in operating room

† Medical Oncologist will prescribe sunitinib and monitor for toxicity during treatment

 If BCG is given locally no specimens need to be obtained at the Week 1 and Week 6 visits.

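### Section 10.2 restarts sunitinib after any drug-related grade 3 or 4 non-hematologic event, while the 10.2.1 table stops it for cardiac grade 3, cardiac grade 4 and neurotoxicity grade 4; removal is the natural reading but is nowhere expressly stated

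*Combined protocol and SAP*

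**What the plan says.** Section 10.2 opens with a general rule. Its trigger is "In the event of any (CTC version 3) drug related grade 3 or 4 non-hematologic or" grade 4 hematologic toxicity (the sentence is split by a table in the extracted text). Its action is that the "drug should be held until the toxicity resolves to < grade 1 and then the drug should be restarted at -1 dose level". No organ system is excepted, and the reader is sent to Section 6.1 for the dose levels.

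Section 10.2.1 then gives a table by toxicity type and grade. For cardiac toxicity of grade 3, cardiac toxicity of grade 4 and neurotoxicity of grade 4 the entry is "Remove from further therapy, follow for applicable endpoints". The table is introduced with the sentence "The following table describes the recommended dose modifications for study treatment associated toxicity".

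Three other texts bear on the choice:

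- The first bullet of 10.2.1 allows reduction by one or two levels "depending on the type and severity of toxicity encountered provided that criteria for patient withdrawal from study treatment have not been met".
- The paragraph on cardiac ejection fraction under 10.2.1 says "Patients with an ejection fraction lower than the institutional lower limit of normal will not receive further study treatment per protocol".
- Section 8.1 removes patients with unacceptable adverse events that "in the judgment of the treating physician make it dangerous for the patient to be retreated".

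A note to the study calendar in Section 13.0 adds: "Medical Oncologist will prescribe sunitinib and monitor for toxicity during treatment".

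**The concern.** For the same event, one text restarts the drug at a lower dose and the other stops it for good. A clinician who followed 10.2 to the letter would give sunitinib again after a resolved grade 3 or 4 cardiac event, or a resolved grade 4 neurologic event. These are the situations in which the table says treatment should end. The stake is patient safety and consistent handling of severe toxicity; the efficacy analysis is not at issue.

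**Working it through.** There is no design figure to reproduce, so the check sets the texts side by side. Taking 10.2 at its literal scope, it covers nine cells of the 10.2.1 table. In every one, 10.2 says to hold until below grade 1 and then restart at level -1.

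| Event | 10.2.1 table | Compared with 10.2 |
|---|---|---|
| Cardiac G3 | Stop | Opposite |
| Cardiac G4 | Stop | Opposite |
| Neurotoxicity G4 | Stop | Opposite |
| Neurotoxicity G3 | Hold to grade 1 or below, reduce one level | Same action, looser threshold |
| Other non-hematologic G3 | Same dose or one level lower, investigator's choice | 10.2 more cautious on dose |
| Other non-hematologic G4 | One level lower or stop, investigator's choice | Table allows stopping; 10.2 does not mention it |
| Flu-like G3 | Same dose once grade 2 or below, or back at baseline | 10.2 more cautious |
| Flu-like G4 | One level lower once grade 2 or below | 10.2 more cautious on threshold |
| Hematologic G4 | One level lower once grade 2 or below | 10.2 more cautious on threshold |

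Three of the nine cells are opposite, and 9 - 3 = 6 do not require removal. The table footnotes add further differences in which 10.2 is again the stricter text: certain laboratory abnormalities without clinical signs may continue uninterrupted, and grade 4 lymphopenia needs no reduction.

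Next, does any other text settle the three opposite cells?

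1. *Withdrawal proviso in 10.2.1.* A restart at level -1 is a dose reduction, and the table entry reads as withdrawal from treatment, so the proviso points to removal. It does not mention 10.2, and it does not call the table entries withdrawal criteria.
2. *Ejection-fraction rule in 10.2.1.* It bars further treatment when the ejection fraction is below the institutional limit. It does not reach a cardiac grade 3 or 4 event without a documented low ejection fraction, and it has no bearing on neurotoxicity.
3. *Section 8.1.* It leaves the decision to the treating physician and names no cardiac or neurologic grade.
4. *Section 7.2, second cycle.* The only toxicity-related condition stated there is a normal MUGA scan, which has the same gaps as item 2.

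All four lean towards removal or are silent. None ranks 10.2 against the table.

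Next, would scheduled monitoring catch a wrong restart? In the Section 13.0 calendar, MUGA and EKG are marked at pre-study only. Weeks 8, 10 and 12, the sunitinib visits, carry history and physical, performance status, medication check and blood tests, but no cardiac test. The next planned MUGA comes before a second cycle. After a cardiac event in cycle 1, the ejection-fraction rule therefore operates only if someone orders an unscheduled scan.

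Next, the cross-references. Both 10.2 and the first bullet of 10.2.1 point to 6.1 for dose levels. That is the BCG table, where level -1 is 25 mg. The sunitinib levels are in 6.2.1, where level -1 is 37.5 mg.

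Last, the effect on the analysis. Section 16.1 counts a patient as evaluable after one dose of sunitinib. A patient removed later for toxicity stays in the analysis set, so the 24 + 12 = 36 patients and the stated error rates are untouched.

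**The case against.** The strongest reply is that the protocol already resolves the conflict. The table is specific and directly follows the general sentence, its entry is imperative, and the proviso makes reduction conditional on withdrawal criteria not being met. Recruitment is from one institution's urology clinics, and a medical oncologist prescribes sunitinib and monitors its toxicity. A wrong restart would need that oncologist to pass over an explicit instruction to stop. It would also need the event to have resolved below grade 1 (10.2) and recovered within four weeks (10.2.1). All of this stands, and it is why removal is the natural reading. What remains is that the result is inferred from several texts, while 10.2 says the contrary in plain terms.

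A second reply is that non-hematologic in 10.2 may mean only the table row of that name. On that reading 10.2 covers three cells (that row at grades 3 and 4, and hematologic grade 4), and none requires removal. This is possible, but 10.2 says any such event, and cardiac and neurologic events are non-hematologic in the ordinary sense.

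Two stronger readings are tempting, and the documents do not support them. A reader might infer that the table is optional because 10.2.1 calls it recommended. Section 10.1.2 introduces the BCG table with the same word, yet that table directs withdrawal for severe infection. A reader might also infer that the table should govern throughout. That would adopt the less cautious rule for flu-like grades 3 and 4, hematologic grade 4, the footnoted laboratory events and grade 4 lymphopenia. It is a clinical trade-off that is not needed to remove the three opposite instructions.

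**Conclusion.** The inconsistency is real and is confined to three cells: cardiac grade 3, cardiac grade 4 and neurotoxicity grade 4. This assumes that 10.2 covers all non-hematologic events, as its wording suggests. Removal is the better reading of the protocol as a whole, but it is implied, and no scheduled cardiac test in cycle 1 backs it up.

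Few patients would be affected. A reader might try to size the risk from Section 11.2, which lists myocardial infarction, seizure and decreased blood flow to the brain among effects seen in under 1% of patients. Those frequencies are not broken down by grade. The documents do not give the share that would be grade 3 or 4, drug-related, resolved below grade 1 within the allowed time and then restarted. Any probability built on them would describe a different event, so none is given here.

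No efficacy result, evaluable set or Section 16 figure changes. The point is still worth fixing because the literal rule leads to an unsafe action and the correction is nearly free.

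**What to change.** Add an exception to the restart sentence in 10.2, for example: *except for cardiac toxicity of grade 3 or 4 and neurotoxicity of grade 4, for which sunitinib is permanently discontinued (see the table in 10.2.1), including in cycle 2 and whatever the MUGA result*. The clinical team should confirm the rule. Change the references to 6.1 in 10.2 and in the first bullet of 10.2.1 to 6.2.1.

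Leave the other differences between 10.2 and the table, including the recovery thresholds, for the clinical team to align as a separate decision.

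The cost is a wording amendment of one clause and two cross-references. Sample size, visits and data collection do not change.

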#### **6.2.4 DOSE REDUCTIONS: Please refer to Section 11.**

#### **6.2.5 SUPPORTIVE CARE GUIDELINES:**

- Diarrhea
  - Lomotil or Imodium may be used by patients developing diarrhea during treatment.
- Hypertension
  - Blood pressure should be well controlled before starting study drug.
  - Standard blood pressure medications should be used for patients that develop hypertension during treatment.
  - Diltiazem and verapamil should be avoided if possible as they are potential inhibitors of the CYP3A4 pathway (see section 6.2.3).
  - If hypertension develops or worsens while on study drug, treatment should first be with optimizing standard anti-hypertensive agents. If refractory, study drug dose modifications can be made.
  - In cases of severe hypertension (>200 mmHg systolic or 110 mmHg diastolic) temporary suspension of study drug is recommended until hypertension is controlled.
- Fatigue
  - For intolerable fatigue, the next cycle of treatment may be delayed by one week.

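### Sections 10.2 and 10.2.1 give different sunitinib instructions for the same severe toxicities, including restart versus removal after grade 3-4 cardiac events, and no text says which governs

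*Combined protocol and SAP*

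**What the plan says.** Section 10.2 opens with a general rule. Its scope begins "In the event of any (CTC version 3) drug related grade 3 or 4 non-hematologic or" and goes on to include grade 4 hematologic events. For all of these, "drug should be held until the toxicity resolves to < grade 1 and then the drug should be restarted at -1 dose level".

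Section 10.2.1 then gives a table by toxicity and grade, introduced with "The following table describes the recommended dose modifications for study treatment associated toxicity". Entries relevant here:

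- Cardiac toxicity at grades 3 and 4, and neurotoxicity at grade 4: "Remove from further therapy, follow for applicable endpoints".
- Other non-hematologic toxicity at grade 3: hold until recovery, "then resume treatment at the same dose level or reduce the dose by 1 level at the discretion of the investigator".
- Hematologic toxicity at grade 4: hold to grade 2 or lower, "then reduce the dose by 1 level and resume treatment".
- Footnotes: "Grade 4 lymphopenia does not require dose reduction". Patients with grade 3 or 4 lipase or amylase elevation and no sign of pancreatitis may stay on drug.

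Both sections send the reader to 6.1 for dose levels. The levels in 6.1.1 are those of BCG (50, 25 and 12.5 mg). The sunitinib levels (50, 37.5 and 25 mg) are in 6.2.1.

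**The concern.** A clinician facing one of these events has two written instructions. The serious case is cardiac. Taken at its word, 10.2 restarts sunitinib at the reduced dose after a grade 3 or 4 cardiac event, while the table ends the drug. Sunitinib has known effects on ejection fraction (sections 2.4 and 11.2), so this is the place where an ambiguous rule is least welcome.

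There is also a consistency problem. Deviations are recorded on a form and sent quarterly to the monitoring board (17.3.1). With two rules in force, removing a patient after a grade 3 cardiac event, or resuming 50 mg after grade 3 flu-like symptoms, complies with one rule and deviates from the other.

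**Working it through.** No arithmetic applies. The check sets the 10.2 rule (hold to below grade 1, restart at level -1) against each entry in 10.2.1 that falls within its scope.

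| Drug-related event | 10.2.1 table or footnote | Can one action satisfy both rules? |
|---|---|---|
| Cardiac, grade 3 or 4 | End sunitinib | No |
| Neurotoxicity, grade 4 | End sunitinib | No |
| Flu-like, grade 3 | Hold to grade 2 or lower, or baseline; same dose | No |
| Flu-like, grade 4 | Hold to grade 2 or lower; down one level | Dose agrees; recovery threshold does not |
| Hematologic, grade 4 | Hold to grade 2 or lower; down one level | Dose agrees; recovery threshold does not |
| Other non-hematologic, grade 3 | Hold to grade 1 or lower, or baseline; same dose or down one level, investigator's choice | Yes on dose, by going down; only resuming at 50 mg departs from 10.2 |
| Other non-hematologic, grade 4 | Hold to grade 1 or lower, or baseline; down one level, or discontinue | Yes on dose, by going down; discontinuing departs from 10.2 |
| Lymphopenia, grade 4 | No reduction required | The footnote waives what 10.2 orders |
| Lipase or amylase, grade 3 or 4, no pancreatitis | May continue uninterrupted | The footnote allows what 10.2 rules out |
| Neurotoxicity, grade 3 | Hold to grade 1 or lower; down one level | Yes on dose |

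The differences are of three kinds. In the first three rows the two dosing instructions exclude each other. In the next two the dose agrees but the recovery threshold differs. In the following four rows, 10.2.1 permits or waives something that 10.2 does not.

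**Could a lost symbol explain it?** The BCG toxicity table falls in the middle of the 10.2 sentence in the text as read from the PDF, but the two halves join grammatically. If the less-than sign in 10.2 was meant as less-than-or-equal, the non-hematologic and grade 3 neurotoxicity thresholds would agree at grade 1. Grade 4 hematologic and flu-like events would still differ (grade 1 against grade 2), and none of the conflicts over dose or removal depends on that symbol.

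**Is precedence stated anywhere?** Section 10.2 applies to any such event and makes no exception for the table. Section 10.2.1 calls its table recommended and does not say that it overrides 10.2. Section 6.2.2 refers to section 10 as a whole. Section 6.2.4 refers to Section 11, which holds pharmaceutical information. None of these chooses between the rules.

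**The case against.** The best defense is that a general sentence followed by an organ-specific table is naturally read as a rule with exceptions, and that most clinicians would take the safer instruction after a cardiac or neurologic event. Several provisions support this. Section 10.2.1 allows dose reduction only while withdrawal criteria are not met. Section 8.1 ends therapy for adverse events that make retreatment dangerous. Section 11.2 lets the investigator suspend or reduce for safety. The study calendar has a medical oncologist prescribe sunitinib and monitor toxicity. A scan before any second course bars further treatment if ejection fraction is below normal.

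Much of this stands, and it makes actual harm unlikely. It does not settle which rule is the protocol. The withdrawal proviso is in 10.2.1, not in 10.2. Section 8.1 and section 11.2 rest on judgment and do not choose between the written rules. The repeat scan comes only before a second course and concerns only ejection fraction, so it does not cover a restart within the first course. None of these provisions touches the flu-like, hematologic or laboratory differences.

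A reader might infer that grade 3 fatigue is the worst case because either dose breaks a rule. The table does not support that: fatigue falls in the general non-hematologic row, where going down one level is an option, so 37.5 mg satisfies both rules. Nor is section 6.2.5 a competing rule. Its wording, "For intolerable fatigue, the next cycle of treatment may be delayed by one week", is permissive, concerns the next cycle and is silent on restart dose; each course contains a single sunitinib cycle (7.2).

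**Conclusion.** Wrong as written, and minor. Two sections give incompatible or differing instructions for the same severe toxicities, and the plan does not say which prevails. The clearest cases are restart versus removal (cardiac grades 3 and 4, neurotoxicity grade 4) and reduced versus same dose (flu-like grade 3). The wrong reference to 6.1 adds to the confusion. The conclusion assumes only that the two halves of the 10.2 sentence belong together and that the word *any* carries its ordinary meaning.

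The size is qualitative. A reader might want to express the difference in milligrams or numbers of patients, but the documents give neither hold times nor grade-specific rates for these events, so such figures would rest on assumption. A reader might also infer that reported results would shift with the rule chosen. Sections 16.2 and 17.1 plan tabulations of toxicity by grade, type, category and body system, not counts of dose reductions or discontinuations. The evaluable set is defined by at least one dose of sunitinib (16.1), so it is the same under either rule. Sample size, error rates and the two-stage decision rule do not depend on it either.

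**What to change.** Replace the opening sentence of 10.2 with:

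*Sunitinib dose modification for drug-related toxicity (CTCAE version 3) follows the table and footnotes in 10.2.1, which govern; grade 3-4 cardiac toxicity and grade 4 neurotoxicity end sunitinib; dose levels are in 6.2.1.*

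Change both sunitinib references to 6.1, in 10.2 and 10.2.1, to 6.2.1. Leave the table entries, the footnotes, the investigator's discretion and section 6.2.5 as they are.

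The change should stop there. In particular, a new rule on the starting dose of a second course is not needed to remove the contradiction. It would also clash with the Protocol Summary (item 4) and section 7.2, which describe that course as identical to the first.

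The cost is one replaced sentence and two corrected references, with no added visits, tests or patients.
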